*Note: "Blinding" subjects to their study group/condition/arm is not considered to be deception, but not telling them ahead of time that they will be subject to an intervention or about the purpose of the procedure(s) is deception.*

No

Yes

→ If yes, describe what information and why.

*Example: It may be necessary to deceive subjects about the purpose of the study (describe why).*

a. Will subjects be informed beforehand that they will be unaware of or misled regarding the nature or purposes of the research? (Note: this is not necessarily required.)

	No
	Yes

b. Will subjects be debriefed later? (Note: this is not necessarily required.)

	No
	Yes

→ If yes, describe how and when this will occur. Upload any debriefing materials, including talking points or a script, to **Zipline**.

**8.8 Cognitively impaired adults, and other adults unable to consent.** Will such individuals be included in the research?

*Examples: individuals with Traumatic Brain Injury (TBI) or dementia; individuals who are unconscious, or who are significantly intoxicated.*

	No
	Yes

→ If no, go to [question 8.9](#).

→ If yes, answer the following questions.

a. Rationale. Provide the rationale for including this population.

b. Capacity for consent / decision making capacity. Describe the process that will be used to determine whether a cognitively impaired individual is capable of consent decision making with respect to the research protocol and setting.

b.1. If there will be repeated interactions with the impaired subjects over a time period when cognitive capacity could increase or diminish, also describe how (if at all) decision-making capacity will be re-assessed and (if appropriate) consent obtained during that time.

c. Permission (surrogate consent). If the research will include adults who cannot consent for themselves, describe the process for obtaining permission ("surrogate consent") from a legally authorized representative (LAR).

*For research conducted in Washington State, see the [GUIDANCE: Legally Authorized Representative](#) to learn which individuals meet the state definition of "legally authorized representative".*

d. Assent. Describe whether assent will be required of all, some, or none of the subjects. If some, indicate which subjects will be required to assent and which will not (and why not). Describe any process that will be used to obtain and document assent from the subjects.

e. Dissent or resistance. Describe how a subject's objection or resistance to participation (including non-verbal) during the research will be identified, and what will occur in response.

**8.9 Research use of human fetal tissue obtained from elective abortion.** Federal and UW Policy specify some requirements for the consent process. If you are conducting this type of research, check the boxes to confirm these requirements will be followed. N/A

- Informed consent for the donation of fetal tissue for research use will be obtained by someone other than the person who obtained the informed consent for abortion.
- Informed consent for the donation of fetal tissue for research use will be obtained after the informed consent for abortion.
- Participation in the research will not affect the method of abortion.
- No enticements, benefits, or financial incentives will be used at any level of the process to incentivize abortion or the donation of human fetal tissue.
- The informed consent form for the donation of fetal tissue for use in research will be signed by both the woman and the person who obtains the informed consent.

**8.10 Consent-related materials.** Upload to **Zipline** all consent scripts/talking points, consent forms, debriefing statements, Information Statements, Short Form consent forms, parental permission forms, and any other consent-related materials that will be used. Materials that will be used by a specific site should be uploaded to that site's **Local Site Documents** page.

- Translations must be submitted and approved before they can be used. However, we strongly encourage you to wait to provide them until the IRB has approved the English versions.
- Combination forms: It may be appropriate to combine parental permission with consent, if parents are subjects as well as providing permission for the participation of their children. Similarly, a consent form may be appropriately considered an assent form for older children.
- For materials that cannot be uploaded: upload screenshots or written descriptions that are sufficient to enable the IRB to understand the types of data that will be collected and the nature of the experience for the participant. URLs (website addresses) may also be provided, or written descriptions of websites. Examples of materials that usually cannot be uploaded: mobile apps; computer-administered test; licensed and restricted standardized tests.

## 9 PRIVACY AND CONFIDENTIALITY

### 9.1 Privacy protections.

**Describe the steps that will be taken, if any, to address possible privacy concerns of subjects and potential subjects.**

*Privacy refers to the sense of being in control of access that others have to ourselves. This can be an issue with respect to recruiting, consenting, sensitivity of the data being collected, and the method of data collection.*

*Examples:*

- *Many subjects will feel a violation of privacy if they receive a letter asking them to participate in a study because they have \_\_\_\_\_ medical condition, when their name, contact information, and medical condition were drawn from medical records without their consent. Example: the IRB expects that “cold call” recruitment letters will inform the subject about how their information was obtained.*
- *Recruiting subjects immediately prior to a sensitive or invasive procedure (e.g., in an outpatient surgery waiting room) will feel like an invasion of privacy to some individuals.*
- *Asking subjects about sensitive topics (e.g. details about sexual behavior) may feel like an invasion of privacy to some individuals.*

The consent form list steps to ensure privacy of information. We will talk with participants about any concerns or questions they have of privacy protections.

### 9.2 Identification of individuals in publications and presentations.

**Will potentially identifiable information about subjects be used in publications and presentations, or is it possible that individual identities could be inferred from what is planned to be published or presented?**

**No**

**Yes** → If yes, will subject consent be obtained for this use?

**Yes**

**No** → If no, describe the steps that will be taken to protect subjects (or small groups of subjects) from being identifiable.

### 9.3 State mandatory reporting.

**Each state has reporting laws that require some types of individuals to report some kinds of abuse, and medical conditions that are under public health surveillance. These include:**

- Child abuse
- Abuse, abandonment, neglect, or financial exploitation of a vulnerable adult
- Sexual assault
- Serious physical assault
- Medical conditions subject to mandatory reporting (notification) for public health surveillance

Are you or a member of the research team likely to learn of any of the above events or circumstances while conducting the research **AND** feel obligated to report it to state authorities?

**No**

**Yes** → If yes, the UW IRB expects subjects to be informed of this possibility in the consent form or during the consent process, unless you provide a rationale for not doing so:

**9.4 Retention of identifiers and data.** Check the box below to indicate assurance that any identifiers (or links between identifiers and data/specimens) and data that are part of the research records will not be destroyed until after the end of the applicable records retention requirements (e.g. Washington State; funding agency or sponsor; Food and Drug Administration). If it is important to say something about destruction of identifiers (or links to identifiers) in the consent form, state something like “the link between your identifier and the research data will be destroyed after the records retention period required by state and/or federal law.”

*This question can be left blank for conversion applications (existing paper applications that are being “converted” into a Zipline application.)*

*See the “Research Data” sections of the following website for UW Records management for the Washington State research records retention schedules that apply in general to the UW (not involving UW Medicine data):*

<http://f2.washington.edu/fm/recmgt/gs/research?title=R>

*See the “Research Records and Data” information in Section 8 of this document for the retention schedules for UW Medicine Records: <https://www.uwmedicine.org/recordsmanagementuwm-records-retention-schedule.pdf>*

**Confirm**

**9.5 Certificates of Confidentiality.** Will a federal Certificate of Confidentiality be obtained for the research data?

*NOTE: Answer “No” if the study is funded by NIH or the CDC, because all NIH-funded and CDC-funded studies automatically have a Certificate.*

**No**  
 **Yes**

**9.6 Data and specimen security protections.** Identify the data classifications and the security protections that will be provided for all sites where data will be collected, transmitted, or stored, referring to the [ZIPLINE GUIDANCE: Data and Security Protections](#) for the minimum requirements for each data classification level. ***It is not possible to answer this question without reading this document. Data security protections should not conflict with records retention requirements.***

a. Which level of protections will be applied to the data and specimens? If more than one level will be used, describe which level will apply to which data and which specimens and at which sites.

**Level 4**

b. Use this space to provide additional information, details, or to describe protections that do not fit into one of the levels. If there are any protections within the level listed in 9.6.a which will *not* be followed, list those here, including identifying the sites where this exception will apply.

**N/A**

## 10 RISK / BENEFIT ASSESSMENT

**10.1** **Anticipated risks.** Describe the reasonably foreseeable risks of harm, discomforts, and hazards to the subjects and others of the research procedures. For each harm, discomfort, or hazard:

- Describe the magnitude, probability, duration, and/or reversibility of the harm, discomfort, or hazard, AND
- Describe how the risks will be reduced or managed. Do not describe data security protections here, these are already described in Question 9.6.
- Consider possible physical, psychological, social, legal, and economic harms, including possible negative effects on financial standing, employability, insurability, educational advancement or reputation. For example, a breach of confidentiality might have these effects.
- Examples of "others": embryo, fetus, or nursing child; family members; a specific group.
- Do not include the risks of non-research procedures that are already being performed.
- If the study design specifies that subjects will be assigned to a specific condition or intervention, then the condition or intervention is a research procedure - even if it is a standard of care.
- Examples of mitigation strategies: inclusion/exclusion criteria; applying appropriate data security measures to prevent unauthorized access to individually identifiable data; coding data; taking blood samples to monitor something that indicates drug toxicity.
- As with all questions on this application, you may refer to uploaded documents.

Participating in a depression research trial may lead to stigma within the subjects' community. We will attempt to mitigate this by providing depression education within the broader community. Additionally, screening and stepped care treatment for depression will be within an app designed to screen for physical health as well, ensuring that women with depression are not singled out.

**10.2** **Reproductive risks.** Are there any risks of the study procedures to men and women (who are subjects, or partner of subjects) related to pregnancy, fertility, lactation or effects on a fetus or neonate?

Examples: direct teratogenic effects; possible germline effects; effects on fertility; effects on a woman's ability to continue a pregnancy; effects on future pregnancies.

	No
	Yes

→ If no go to [question 10.3](#)

→ If yes, answer the following questions:

**a. Risks.** Describe the magnitude, probability, duration and/or reversibility of the risks.

**b. Steps to minimize risk.** Describe the specific steps that will be taken to minimize the magnitude, probability, or duration of these risks.

Examples: inform the subjects about the risks and how to minimize them; require a pregnancy test before and during the study; require subjects to use contraception; advise subjects about banking of sperm and ova.

If the use of contraception will be required: describe the allowable methods and the time period when contraception must be used.

**c. Pregnancy.** Describe what will be done if a subject (or a subject's partner) becomes pregnant

For example; will subjects be required to immediately notify study staff, so that the study procedures can be discontinue or modified, or for a discussion of risks, and/or referrals or counseling?

**10.3 MRI risk management.** Answer this question only if the subjects will receive MRI scans. A rare but serious adverse reaction called nephrogenic systemic fibrosis (NSF) has been observed in individuals with kidney disease who received gadolinium-based contrast agents (GBCAs) for the scans. Also, a few healthy individuals have a severe allergic reaction to GBCAs.

a. Describe how the renal function of subjects will be assessed prior to MRI scans and how that information will be used to exclude subjects at risk for NSF.

N/A

b. Describe the protocol for handling a severe allergic reaction to the GBCA or any other medical event/emergency during the MRI scan, including who will be responsible for which actions.

N/A

**10.4 Unforeseeable risks.** Are there any research procedures that may have risks that are currently unforeseeable?

*Example: using a drug that hasn't been used before in this subject population.*

	No
	Yes

→ If yes, identify the procedures.

**10.5 Subjects who will be under regional or general anesthesiology.** Will any research procedures occur while patients are under general or regional anesthesia, or during the 3 hours preceding general or regional anesthesia (supplied for non-research reasons)?

	No
	Yes

→ If yes, check all the boxes that apply.

	Administration of any drug for research purposes
	Inserting an intra-venous (central or peripheral) or intra-arterial line for research purposes
	Obtaining samples of blood, urine, bone marrow or cerebrospinal fluid for research purposes
	Obtaining a research sample from tissue or organs that would not otherwise be removed during surgery
	Administration of a radio-isotope for research purposes**
	Implantation of an experimental device
	Other manipulations or procedures performed solely for research purposes (e.g., experimental liver dialysis, experimental brain stimulation)

If any of the boxes are checked:

Provide the name and institutional affiliation of a physician anesthesiologist who is a member of the research team or who will serve as a safety consultant about the interactions between the research procedures and the general or regional anesthesia of the subject-patients. If the procedures will be performed at a UW Medicine facility or affiliate, the anesthesiologist must be a UW faculty member, and the Vice Chair of Clinical Research in the UW Department of Anesthesiology and Pain Medicine must be consulted in advance for feasibility, safety and billing.

*\*\* If the box about radio-isotopes is checked: the study team is responsible for informing in advance all appropriate clinical personnel (e.g., nurses, technicians, anesthesiologists, surgeons) about the administration and use of the radio-isotope, to ensure that any personal safety issues (e.g., pregnancy) can be appropriately addressed. This is a condition of IRB approval.*

**10.6 Data and Safety Monitoring.** A Data and Safety Monitoring Plan (DSMP) is required for clinical trials (as defined by NIH). If required for this research, or if there is a DSMP for the research regardless of whether it is required, upload the DSMP to **Zipline**. If it is embedded in another document being uploading (for example, a Study Protocol) use the text box below to name the document that has the DSMP. Alternatively, provide a description of the DSMP in the text box below.

DSMP has been uploaded

**10.7 Un-blinding.** If this is a double-blinded or single-blinded study in which the participant and/or relevant study team members do not know the group to which the participant is assigned: describe the circumstances under which un-blinding would be necessary, and to whom the un-blinded information would be provided.

N/A – app based study – participants will know what intervention they are getting

**10.8 Withdrawal of participants.** If applicable, describe the anticipated circumstances under which participants will be withdrawn from the research without their consent. Also, describe any procedures for orderly withdrawal of a participant, regardless of the reason, including whether it will involve partial withdrawal from procedures and any intervention but continued data collection or long-term follow-up.

Participants will be withdrawn from the trial in case of emergent suicidal ideation or new psychosis as they will be directed to a higher level of care.

**10.9 Anticipated direct benefits to participants.** If there are any direct research-related benefits that some or all individual participants are likely to experience from taking part in the research, describe them below:

*Do not include benefits to society or others, and do not include subject payment (if any). Examples: medical benefits such as laboratory tests (if subjects receive the results); psychological resources made available to participants; training or education that is provided.*

All participants will receive standardized depression education. Participants randomized to the intervention will receive the MITHRA intervention for the treatment of depression.

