**4.6 Will data or specimens be accessed or obtained for recruiting and screening procedures prior to enrollment?**

*Examples: names and contact information; the information gathered from records that were screened; results of screening questionnaires or screening blood tests; Protected Health Information (PHI) from screening medical records to identify possible subjects.*

	No
	Yes

→ If no, skip the rest of this section; go to [question 5.1](#).  
→ If yes, describe the data and/or specimens (including PHI) and whether it will be retained as part of the study data.

For the CBO participant focus groups in Aim 1, potential participants will receive a paper based PHQ-9 to enable recruitment of up to 3 women with PHQ-9 scored of more than 5. The paper PHQ-9s will not have identifying information and will be shredded immediately after the CHW has determined the total scores. We will however maintain a count of how many women were prescreened and how many of them had a score of more than 5. For the RCT we will administer PHQ-9 to all attendees of the CBO using the same talking points, to identify CBOs with more than one woman who scores positive on the PHQ-9.

**4.7 Consent for recruiting and screening.** Will consent be obtained for any of the recruiting and screening procedures? ([Section 8: Consent of Adults](#) asks about consent for the main study procedures).

“Consent” includes: consent from individuals for their own participation; parental permission; assent from children; consent from a legally authorized representative for adult individuals who are unable to provide consent.

Examples:

- For a study in which names and contact information will be obtained from a registry: the registry should have consent from the registry participants to release their names and contact information to researchers.
- For a study in which possible subjects are identified by screening records: there will be no consent process.
- For a study in which individuals respond to an announcement and call into a study phone line: the study team person talking to the individual may obtain non-written consent to ask eligibility questions over the phone.

No

→ If no, skip the rest of this section; go to [question 5.1](#).

Yes

→ If yes, describe the consent process.

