CHWs will administer the PHQ9, if more than one woman PHQ9 positive then CHW will proceed with informed consent for all members of SHG. The CHW will use the attached talking points to obtain verbal consent from participants.

a. Documentation of consent. Will a written or verifiable electronic signature from the subject on a consent form be used to document consent for the recruiting and screening procedures?

No

→ If no, describe the information that will be provided during the consent process and for which procedures.

Yes

→ If yes, upload the consent form to [Zipline](#).

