Randomized trial: We will randomize CBOs to use MITHRA (n=3) or enhanced usual care (EUC) (n=3) for 12 weeks. Randomization will be clustered to account for distance from the PHC. The MITHRA CBOs will each have 2 -3 tablets for use by all attendees. A CHW will be present at meetings and encourage women to use the MITHRA app. During their time at the meeting, women will complete the PHQ-9 screening and modules based on their individual depression score. Privacy will be ensured. They will also have the option to take turns checking out the tablet for viewing at home (if this is reported by the design group to be a desirable feature). In the EUC CBOs, CHWs will offer monthly group education (45 min) regarding the symptoms of depression, informed by training webinars led by study Investigators. We have the support of the CBO and PHC leadership for this project (see attached letters of support). In both MITHRA and EUC CBOs CHWs will conduct community outreach to encourage women to attend meetings, as depression can lead to amotivation and women with depression may be less likely to attend CBO meetings. All CHWs will receive training in depression, screening and common treatments, resources and referrals.

**Outcome Measures:** CHWs will maintain rosters of CBO attendees at MITHRA CBOs and EUC CBOs. In monthly review sessions with the study investigators, the CHWs will review questionnaire completion and scores, and directly contact the woman (by phone or home visit or at a CBO meeting) if there is a need to step up care beyond that advised by the app. Women typically attend CBO meetings 2 -3 times a month and use at every attendance will be encouraged.

**MITHRA** is an app which will be available on 2 -3 tablets placed in Community Based Organizations (CBOs). Women can log in to MITHRA using a unique password protected secure single user sign on (fingerprint sign in to account for varying levels of literacy) to complete the physical health questionnaire and the PHQ -9 (validated Kannada version of the PHQ-9) in an assigned private place in the CBO. On completion of the PHQ-9, each woman will receive a prompt based on her total score (see Fig). Women who score < 5 will watch general information on depression; women who score 5 – 10 will watch modules 1 and 2 (case descriptions, What is Depression? and Introduction to PHQ-9) Women who score 10 – 15 will watch modules 1, 2, and 3 (Connection between activity and mood).

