**a. Is it anticipated that the research will produce any individual research results that are clinically actionable?**

“Clinically actionable” means that there are established therapeutic or preventive interventions or other available actions that have the potential to change the clinical course of the disease/condition, or lead to an improved health outcome.

In general, every effort should be made to offer results that are clinically actionable, valid and pose life-threatening or severe health consequences if not treated or addressed quickly. Other clinically actionable results should be offered if this can be accomplished without compromising the research.

	No
	Yes

→ If yes, answer the following questions (a.1-a.3).

**a.1. Describe the clinically actionable results that are anticipated and explain which results, if any, could be urgent (i.e. because they pose life-threatening or severe health consequences if not treated or addressed quickly).**

Examples of urgent results include very high calcium levels, highly elevated liver function test results, positive results for reportable STDs.

Research assessments include measures of depression which may indicate depression which will need treatment. We will inform subjects who score above the clinical cut off the results of their questionnaire and advise them to share these results with their primary care provider and seek treatment for depression. For all subjects, whether they score above the cut off or not, anyone who scores anything other than 0 on the 9th question of the PHQ-9 will be informed of this and will receive further assessment / intervention as outlined in the attached suicidality protocol.

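### Section 10.8 withdraws women from the trial for emergent suicidal ideation or new psychosis without saying whether their 3- and 6-month outcomes are still collected

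*Combined protocol and SAP*

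**What the plan says.** **The rule.** Section 10.8 (Withdrawal of participants) says: "Participants will be withdrawn from the trial in case of emergent suicidal ideation or new psychosis", and gives the reason: "as they will be directed to a higher level of care". The form's question asks for the withdrawal procedure, "including whether it will involve partial withdrawal from procedures and any intervention but continued data collection or long-term follow-up". The answer does not take up that part.

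**The outcomes at risk.** Section 5.4 schedules QIDS-SR (by a masked assistant) and mental health service use at baseline, 3 and 6 months, and has BADS given to all women. The Statistical Methods section compares the outcome scores between arms at each assessment (t test or Mann-Whitney), examines change at 3 and 6 months, and adds a repeated-measures ANOVA. It states no missing-data method, analysis population or rule for withdrawn women.

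**How ideation is detected.**
- Before consent, in all CBOs (4.6, 4.7): "For the RCT we will administer PHQ-9 to all attendees of the CBO using the same talking points"; "CHWs will administer the PHQ9, if more than one woman PHQ9 positive then CHW will proceed with informed consent for all members of SHG".
- During the 12 weeks, MITHRA (5.1): women complete the PHQ-9 in the app at meetings they typically attend two or three times a month. Any non-zero answer to item 9 alerts the CHW, who calls to make a risk assessment.
- During the 12 weeks, EUC (5.1): monthly group education. No repeated PHQ-9 is described.
- Both arms: outreach by CHWs (5.1), and "All CHWs will receive training in depression, screening and common treatments, resources and referrals". Under 10.10, any subject with a non-zero item 9 "will receive further assessment / intervention as outlined in the attached suicidality protocol".

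**Documents not supplied.** Section 10.6 says only "DSMP has been uploaded". The suicidality protocol named in 10.10 was also filed separately.

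**The concern.** Stopping a study intervention and stopping measurement are different decisions. Section 10.8 merges them, and nothing else in the supplied text separates them again. Two consequences follow.

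1. **Service use.** By 10.8's own reason, the women removed are those being sent to more intensive care. Contact with mental health providers is a listed outcome, so the rule removes women in whom that contact is expected. This needs no imbalance between arms.
2. **Depression scores.** Suicidal ideation goes with more severe depression, so the missing scores would tend to be high. If withdrawals were also more frequent in MITHRA, because only that arm has repeated PHQ-9 screening between research visits, the remaining MITHRA women would look better than the arm as a whole.

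**Working it through.** The plan gives no ideation rate, withdrawal rate, SD or power calculation, so there is no figure to reproduce. Every rate below is an assumption, used to show a range.

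**Inputs.** About 60 women (1.5, 2.7), taken as 30 per arm. Three CBOs per arm for 12 weeks (5.1). Assumed: a net excess of 1, 2 or 3 withdrawals among 30 women.

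**1. Service use.** Let *k* of 30 women truly have contact, *w* be withdrawn, and a share *a* of those withdrawn have had contact. The observed proportion is (*k* − *a·w*)/(30 − *w*).

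| *k* (true %) | *w* = 1, *a* = 0.5 | *w* = 3, *a* = 1 |
|---|---|---|
| 3 (10%) | 2.5/29 = 8.6% | 0/27 = 0% |
| 6 (20%) | 5.5/29 = 19.0% | 3/27 = 11.1% |
| 9 (30%) | 8.5/29 = 29.3% | 6/27 = 22.2% |

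The under-count runs from 30 − 29.3 = 0.7 points to 10 − 0 = 10 points. The 10-point case has all three women with contact withdrawn.

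**2. Score comparison at 3 months.** If withdrawn women score *D* SD above the rest of their arm, and the net excess fraction in MITHRA is *w*/30, the spurious difference in favour of the app is (*w*/30) × *D*.

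| Net excess | *D* = 0.7 | *D* = 1.0 | *D* = 1.5 |
|---|---|---|---|
| 0 | 0 | 0 | 0 |
| 1 of 30 | 0.023 | 0.033 | 0.050 |
| 2 of 30 | 0.047 | 0.067 | 0.100 |
| 3 of 30 | 0.070 | 0.100 | 0.150 |

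For scale, 30 v 30 detects 0.74 SD with 80% power at two-sided 5%, ignoring clustering: 0.150/0.74 = 0.20. Analysed by CBO (3 v 3, 4 df, 10 women each, ICC assumed 0 to 0.10), the detectable difference is about 0.97 to 1.34 SD: 0.150/0.97 = 0.15 and 0.150/1.34 = 0.11.

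**3. Change from baseline.** What matters is the gap at 3 months minus the gap at baseline.
- If these women were nearly as far above the rest at baseline (difference in gaps 0 to 0.3 SD), the bias is at most (3/30) × 0.3 = 0.03 SD.
- If ideation marks worsening, it is larger. Suppose the fraction *f* with the highest ideation is removed from one arm, and ideation correlates 0.6 with the 3-month score and 0.2 to 0.4 with baseline. For normal scores the bias is (0.6 − baseline correlation) × φ(*z*)/(1 − *f*), where *z* cuts off the upper fraction *f*. The last factor is 0.077 for 1/30 and 0.195 for 3/30. The bias then runs from 0.2 × 0.077 = 0.015 to 0.4 × 0.195 = 0.078 SD.

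The range is therefore about 0 to 0.08 SD, depending on how much these women worsened.

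**4. Six months.** Not calculated. The described app use lasts 12 weeks, so the difference in screening ends at about the 3-month visit. A PHQ-9 completed then would bring the 10.10 item 9 response into play in both arms, and later losses could partly even out.

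**The case against.** **An excess in MITHRA is inferred, not stated.** A reader might infer that repeated app screening means more women removed from MITHRA. The documents do not support that as a fact. A non-zero item 9 leads to a call, a risk assessment and an escort to the PHC if needed (5.1), or to further assessment or intervention (10.10). Neither section makes it automatic withdrawal, and 10.8 does not define emergent ideation. Detections are therefore an upper bound on withdrawals. Screening before consent and the baseline assessment are common to both arms, the monthly CHW score reviews in 5.1 are not expressly limited to MITHRA, and no app route for detecting psychosis is described. Recent suicide attempts and severe mental illness are excluded (2.2), and an app that reduced ideation could shrink or reverse the imbalance. All of this stands, and it makes 3 of 30 an unsupported upper end.

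**The missing documents may already settle it.** The DSMP and the suicidality protocol are natural places for such a rule. If either has it, a citation in 10.8 is enough.

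**The bias is small for an exploratory 3 v 3 feasibility trial.** True of the scores: with 30 v 30 the standard error of a difference is √(2/30) = 0.26 SD before clustering. It does not answer the service-use loss, which needs no imbalance.

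**It may be too late.** The Statistical Methods section is in the past tense. If follow-up has ended, no assessments can be added.

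**Conclusion.** The gap in 10.8 is real. As written, the rule ends trial participation, leaves the form's own question on data collection unanswered, and puts at risk outcomes related to both depression severity and service use.

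The service-use effect is the firmer part: an under-count of 0.7 to 10 points if 10 to 30% of 30 women have contact and 1 to 3 are withdrawn, half to all of them with contact. The lean at 3 months, 0.02 to 0.15 SD towards the app, depends on an assumed net excess of 1 to 3 of 30 in MITHRA and is 0 if withdrawals are equal. Bias in change from baseline is about 0 to 0.08 SD under the assumed gaps and correlations.

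Three stronger readings go beyond the documents: that MITHRA will lose more women, that the 6-month comparison also favours the app, and that comparisons of change are safe. The first is only possible, the second is uncertain once app screening stops, and the third fails if ideation reflects worsening. Severity is minor to moderate.

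**What to change.** Leave clinical care, referral and the ending of the intervention to the investigators. On the data side:

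1. State in 10.8 that ending the intervention does not end follow-up. The already scheduled 3- and 6-month assessments (QIDS-SR by the masked assessor, BADS, service use) are still collected from women able to take part in a consent discussion and willing to continue. If the DSMP or suicidality protocol already says this, cite it instead.
2. Analyse each woman in her CBO's allocated arm, and report withdrawals with reasons by arm.
3. Reconcile 5.1, 10.8 and 10.10 on what leads to withdrawal, so that counts by arm can be interpreted.

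If follow-up is already complete, only the analysis and reporting parts apply.

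**Cost:** a short protocol and consent amendment, and at most two already scheduled phone or PHC assessments for a few women, with ability to consent checked first. Some will decline or be unable, so some missing data will remain.
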